## **STUDY PROCEDURES**

**Overview:** The Overview of Study Design table (Table 1) summarizes the frequency and timing of the clinical, imaging, treatments, and other exploratory measurements applicable to this study. Below lists in further detail all procedures involved in the study.

### **Interviews and Ratings**

*Cognitive Assessment:* Participants will be interviewed in a dedicated room at the BCM Greenpark I building. The cognitive assessment tool that will be used is the MATRICS assessment. The full MATRICS battery targets the six cognitive domains (speed of processing; attention/vigilance; working, visual and verbal memory; reasoning and social cognition) identified as being disturbed in schizophrenia. The MATRICS battery takes approximately 1.5 hours.

*Clinical Assessments:* In addition to detailed demographic information (including medication and treatment information), we will obtain diagnostic information using the Structured Clinical Interview for DSM-V Disorders and/or the M.I.N.I diagnostic neuropsychiatric interview (M.I.N.I 7.0.2) at the discretion of the PI. Psychopathological ratings are conducted include: the Brief Psychiatric Rating Scale (BPRS), the Scale for the Assessment of Positive Symptoms (SAPS), the Scale for the Assessment of Negative Symptoms (SANS), the 7-point Clinical Global Impression (CGI) Scale, the Global Assessment of Functioning (GAF). IQ will be assessed using the Wechsler Test of Adult Reading (WTAR) or the Spanish Word Accentuation Test for Spanish speaking patients.

*Medical assessments:* A medical history will be obtained from all participants.

### **Experimental Procedures**

*tDCS:* Participants will undergo two 20 minute daily sessions, separated by 1 hour, for 5 consecutive days. All sessions will be hosted at the Greenpark One site. Identical electrode montages will be applied across all conditions/groups. Given the mechanistic emphasis of the study on target engagement and in order to map effects unambiguously, prefrontal stimulation will be applied in isolation. DLPFC involvement in cognitive control does not show consistent hemispheric lateralization and complex compensatory responses to unilateral stimulation are believed to underlie the variable responses observed in cognitive paradigms. Accordingly, we will stimulate left and right DLPFC simultaneously. This will be achieved by positioning two “active” anodic electrodes on the scalp, placed over F3 and F4 10-20 system electrode sites and two electrodes on the deltoid muscles. This montage was validated by computational models of current flow to robustly target DLPFC.

tDCS will be delivered by a constant-current multi-channel stimulator (NeuroMod tXES Stimulator, RGN, New Mexico, USA) through conductive-rubber electrodes placed in sponges saturated with saline (0.9% NaCl). Micro-processor-controlled current outflow, with independent impedances monitoring and voltage adjustments, will ensure the safe application of identical currents through PFC regions. For the active tDCS groups, constant

current will be applied at the specified level, with 20 sec fade-in and fade-out. The sham group will undergo identical procedures except for the stimulation (aside from the fade-in/fade-out) and will consist of brief (1 second) low current (0.11 mA) pulses every 10 seconds. This differs from sham procedures used in other studies in order to ensure a more reliable control condition.

*Cognitive testing and EEG:* Cognitive effects will be evaluated to assess acute effects compared to baseline and to evaluate their persistence. Subjects will be asked to do some simple tasks which will involve looking at a computer screen display (figures, symbols, numbers, letters, words or sentences) or listening to sounds through headphones (clicks, beeps, or words). The participant is asked to respond to the stimuli by pressing a response button. Stimuli will be presented on a computer screen using E-Prime (Psychological Software Tools, Pittsburgh, PA). Dependent variables will be reaction time, response, and accuracy collected via keyboard, joystick, button box or similar device and stored on a computer. The task will involve separate trials and trials are organized in blocks so that participants will be allowed to rest in between blocks. In each session, cognitive tasks will be presented on a computer screening using E-Prime (Psychology Software Tools, Pittsburgh, PA). EEG will be administered with concurrent high-density (64 channel) EEG acquisition (BrainAmp MRPlus, Brain Products, Munich, Germany) system. This system is CE certified.

*MRI:* Subjects will undergo MRI in order to assist localization of EEG data and provide independent and complementary correlates of tDCS effects. A technician will place the head-coil on the subject, which is like wearing a helmet. The subject will be asked position themselves on a platform that slides inside a large tube (the MRI machine). The subject will be asked to perform computer tasks while in the MRI scanner. These tasks maybe similar in nature to the ones performed during EEG. Participant will be given specific instructions before the session and again for each task before it begins. The scanning session will include both functional and structural MR images. MRI sequences will involve full brain scans - high-resolution structural T1 weighted sequence and functional EPI during task performance as in EEG. Resting state fMRI and DTI may also be acquired. Functional Magnetic Resonance Spectroscopy (MRS) may also be acquired.

### **Location of Study Procedures Across Sites:**

Participants who are recruited through BCM will ONLY complete study procedures at BCM. The participants who are recruited through the MEDVAMC will complete consent and screening procedures at the MEDVAMC. While EEG and tDCS equipment are being acquired and set-up (both should be acquired at the MEDVAMC site approximately by November 2018), MEDVAMC participants will complete EEG and tDCS at the BCM Greenpark location as to not delay the participation of these subjects. The MEDVAMC participants will use the consent form in H-43556, which is specific to the VA and outlines the exact location of each of the procedures.

Once the EEG and tDCS equipment is fully functional at the MEDVAMC, an amendment will be made to the BCM and MEDVAMC protocols and consents indicating that EEG and tDCS will be taking place at the MEDVAMC for the Veterans. At that point, the Veteran participants will be able to complete the majority of the study procedures at the MEDVAMC, with the exception of fMRI. Due to scanner specificity, the fMRI portion of this study will remain at the BCM CAMRI location for the foreseeable future.

### **National Institute of Mental Health Data Archive (NDA)**

Data from this study will be submitted to the National Institute of Mental Health Data Archive (NDA). NDA is a data repository run by the National Institute of Mental Health (NIMH) that allows researchers studying mental illness to collect and share deidentified information with each other. A data repository is a large database where information from many studies is stored and managed. Deidentified information means that all personal information about research participants such as name, address, and phone number is removed and replaced with

a code number. With an easier way to share, researchers hope to learn new and important things about mental illnesses more quickly than before.

During and after the study, the researchers will send deidentified information about participant's health and behavior to NDA. Other researchers nationwide can then file an application with the NIMH to obtain access to the deidentified study data for research purposes. Experts at the NIMH who know how to protect health and science information will look at every request carefully to minimize risks to participant privacy.

Participants may not benefit directly from allowing their information to be shared with NDA. The information provided to NDA may help researchers around the world treat future children and adults with mental illnesses so that they have better outcomes. NIMH will also report to Congress and on its web site about the different studies that researchers are conducting using NDA data. However, participants will not be contacted directly about the data they contributed to NDA.

Participants may decide now or later that they do not want to share their information using NDA. If so, research participants will need to contact the researchers who conducted this study and the researchers will tell NDA, which can stop sharing the research information. However, NDA cannot take back information that was shared before the participant changed their mind. More information about the NDA is available online at <http://data-archive.nimh.gov>.

## **ASSESSMENT OF RISK AND SAFETY**

**Clinical Assessments:** Clinical and neuropsychological assessments are all performed by trained research personnel to reduce the risk of distress from psychiatric interviews and experimental procedures.

**Confidentiality:** Another potential risk is the possibility of loss of confidentiality in case information is lost or misplaced. All protected health information (PHI) will be kept in locked drawers or password protected storage on computers.

**tDCS:** Side effects associated with tDCS procedures include a tingling or itching sensation on the scalp. Very rarely, there may be heating and even burning of skin. The subject will be asked to provide feedback about the degree of comfort and will be able to speak with experimenters at all times. In the rare event the subject find the stimulation highly discomforting or intolerable, the stimulation will be promptly stopped. If the subject is unwilling to resume the protocol, they may withdraw from the study.

**EEG:** The electroencephalography (EEG) system is not FDA approved, but CE certified. It is a non-invasive procedure which may cause skin irritation from the placement of recording electrodes in less than 1% of people. Itchiness of scalp or redness because of electrode gel could result and has the same amount of risk as saline solution. The EEG is administered by trained research staff and can be stopped at any time if the subject becomes uncomfortable.

**MRI:** MRI is very safe, with no radiation or contrast media involved. The procedure has the same risk as a clinical MRI. The only risks of the procedure would be in the event that the patients have metal particles in their body, which if mobile could act as projectiles, or be mechanically activated or displaced if implants. These risks will be minimized using systematic procedures and well-trained technicians, with very careful screening for metal and implants prior to scanning. Claustrophobic reactions can make participation impossible for some subjects. History suggesting of a predisposition will be investigated. However discomfort could arise within the bore even

in absence of positive history. The technician will make sure the individual is comfortable before starting the imaging. During the MRI, the subject will hold onto a ball that sounds an alarm when squeezed and will be instructed to do so if he/she becomes uncomfortable during the procedure. If that happens, the technician will stop the scan to check on the participant.

Importantly, any unanticipated problems will be reported to IRB immediately (within 24 hours). The research team will meet on a weekly basis to review study safety issues, adverse events, data integrity and any other relevant study issues. Any significant concerns or issues during the conduct of the study will be immediately communicated to the study PI. In addition, we will immediately report all of the above to our Data and Safety Monitoring Board (DSMB).

### **Provision of Care to Research Participants and Risk Management**

**Study Discontinuation:** Participants can be discontinued from the research protocol at the PI's discretion due to medical contraindications, intolerable adverse reactions, lack of adherence to study procedures, or clinical deterioration that places participants at risk.

**Poor Adherence:** If a participant misses one tDCS appointment, the PI will allow the participant to remain in the study as long as there are no further missed tDCS appointments. The missed tDCS appointment must be made up for with one additional visit for a total of 10 tDCS sessions, per protocol requirements. Non-adherent participants will be discontinued from the study.

**Methods to Decrease Attrition:** (1) Providing a subject remuneration totaling \$240 for participant's time. (2) Offering flexibility in scheduling to work around school or work schedules (3) Snacks and refreshments at visits.

**After-Care:** Participants who complete the study and those who drop-out for any reason including lack of response or side effects are referred back to their usual providers.

### **STATISTICAL METHODS**

**Primary Objective:** Dependent measures will be task condition-related differences in fMRI BOLD activation as measured through GLM and EEG oscillatory activity in the gamma band as analytically estimated by complex wavelet transformation. Group and time point differences will first be assessed with omnibus tests instantiated through the general linear model (e.g., repeated measures ANOVA) to determine the presence and direction of potential effects. Effects equivalent to  $f \geq .16$  will be targeted. To determine the efficacy of the treatment conditions, we plan to conduct post-hoc comparisons of the post- minus pre-test differences between each active stimulation group and the sham stimulation group, as well as within each group between the post- and pre-test measures. The behavioral context of these changes will also be assessed by the Inc-Con difference in accuracy and reaction time in an analogous manner to fMRI and EEG measures.

**Secondary Objective:** Initial analytical targets will be identified concurrent with Aim 1. Polynomial trend analyses will be used to determine the dose-response curve to tDCS. To assess the degree of efficacy of each treatment, Cohen's  $d_z$ , a measure of effect size similar to Cohen's  $d$  which also accounts for the covariance between measures, will be calculated within each group based on the difference between control-related activations from the pre- and post-test assessments with an ideal target of  $d_z = .534$  for fMRI BOLD activation and  $d_z = .687$  for EEG gamma synchrony (i.e., half the observed distance between patient and control measures based on preliminary data). As an exploratory analysis, we will also make use of the structural MRIs to create individualized head models of current strength in the DLPFC. Since the current strength, distribution and even polarity can vary considerably as a function of individual physiology and anatomy, such comparisons between the predictive value of the tDCS device's current output vs. the modeled current strength in relation to the fMRI

and EEG measures will be invaluable in informing future investigations of personalized treatment protocols and tDCS tolerability/safety.

**Tertiary Objective:** A target completion rate of 80% serves as our benchmark for assessing feasibility. No analysis is required - this benchmark will simply serve as the required threshold for starting the R33 phase.

**R61 to R33 Phase Transition Criteria:** Our 'Go/No-go' strategy for this transition will require an effect size of tDCS to be  $f \geq .16$  for both DLPFC BOLD signal and frontal EEG gamma activity. After confirming that this effect is driven by tDCS effects in a positive direction, the current strength that has the highest effect size *and* also meets >80% completion rate will be the one that is selected for the R33 phase.

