## OBJECTIVES AND HYPOTHESES

100 participants will undergo screening, and upon successful screening, be randomized to one of four treatment groups: 0mA (sham), 1.5mA, 2mA, and 2.5mA. Baseline measures of fMRI and EEG are taken before tDCS treatment. tDCS treatment is twice daily for five consecutive days. Following the last tDCS treatment, a posttest fMRI and EEG is conducted.

An overview of the study design is provided below:

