## OVERVIEW OF STUDY DESIGN

We aim to investigate transcranial Direct Current Stimulation (tDCS) as a novel therapeutic for cognition in psychosis. We will recruit 100 early phase schizophrenia patients with cognitive control deficits. A range of current strengths will also be explored, ranging from 1.5 to 2.5 mA in 0.5 mA increments. Thus, the subjects will be divided into four groups of N=25 for each of the tDCS current strengths including a sham stimulation (placebo) group.

We will recruit equal numbers of female and male participants. Subjects will have less than five years of treatment history and currently be on stable doses of second-generation antipsychotic medications for at least one month. Antipsychotic exposure history will be fully assessed and converted into standardized equivalents. The total duration of this study will be approximately 2 weeks. However, the majority of the study will be within a one week period.

Table 1: Overview of Study Design								
Procedure	Screening	Day 1	Day 2	Day 3	Day 4	Day 5	Day 6	Week 1
Medical, Medication History, Demographics, Color-blind screening	X							
Urine Screen	X							
MRI Screening Form	X							
Clinical Assessments	X							
Cognitive Assessments	X							
fMRI		X						X
EEG		X						X
tDCS			X	X	X	X	X	
Tolerability Assessment			X	X	X	X	X	
Comprehension Assessment	X	X	X	X	X	X	X	X
Payment	\$40	\$75	\$10	\$10	\$10	\$10	\$10	\$75
Total								\$240

**Screening:** Participants who provide written informed consent will undergo screening procedures and a review of the study eligibility criteria. At this visit the participant will complete the initial screening process, which includes detailed demographic information (including medication and treatment information), diagnostic information using the M.I.N.I diagnostic neuropsychiatric interview (M.I.N.I 7.0.2). Additionally, a cognitive assessment, MATRICS, will be conducted to assess level of cognitive functioning. Psychopathological ratings that are conducted include: the Brief Psychiatric Rating Scale (BPRS), the Scale for the Assessment of Positive Symptoms (SAPS), the Scale for the Assessment of Negative Symptoms (SANS) the 7-point Clinical Global Impression (CGI) Scale, the Global Assessment of Functioning (GAF). If participants meet the inclusion/exclusion criteria (see section Subject Population), participants continue to next visit.

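### Active-versus-sham contrasts on raw post-minus-pre change are valid but usually less precise than contrasts adjusted for the pre-test value; the go/no-go is unaffected by adjusting only if its inputs are tied to the unadjusted analyses

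*Combined protocol and SAP*

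**What the plan says.** All references are to the combined protocol and SAP.

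- **STATISTICAL METHODS, Primary Objective.** The first step is: "Group and time point differences will first be assessed with omnibus tests instantiated through the general linear model (e.g., repeated measures ANOVA"). Efficacy of the treatment conditions is then judged by "post-hoc comparisons of the post- minus pre-test differences between each active stimulation group and the sham stimulation group", together with post-versus-pre tests inside each arm. For behaviour, "The behavioral context of these changes will also be assessed by the Inc-Con difference in accuracy and reaction time in an analogous manner" to the imaging and EEG measures.
- **STATISTICAL METHODS, Secondary Objective.** "Polynomial trend analyses will be used to determine the dose-response curve to tDCS". Within-arm d_z is also calculated, with targets of .534 (fMRI) and .687 (EEG).
- **OBJECTIVES AND HYPOTHESES.** "Baseline measures of fMRI and EEG are taken before tDCS treatment".
- **OVERVIEW OF STUDY DESIGN.** "the subjects will be divided into four groups of N=25 for each of the tDCS current strengths including a sham stimulation (placebo) group".
- **R61 to R33 Phase Transition Criteria.** "Our 'Go/No-go' strategy for this transition will require an effect size of tDCS to be" at least .16 on both BOLD and gamma. A positive direction must then be confirmed, and "the current strength that has the highest effect size" is chosen among strengths with more than 80% completion.

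No covariate is named for any of these analyses. The general-linear-model wording, with repeated-measures ANOVA given only as an example, neither requires nor excludes one.

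**The concern.** With two time points, the group-by-time test in a repeated-measures ANOVA is the same test as an ANOVA of change. The omnibus step therefore adds no baseline adjustment, and the follow-up contrasts are on raw change as well. Raw change fixes the slope of post on pre at 1; a covariate model estimates it. If the true slope is below 1, the change score carries avoidable pre-test noise into every comparison between arms.

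Arms are small: 25 each, or about 20 at the 80% completion benchmark. Allocation is matched on demographics and cognitive status, not on pre-test BOLD or gamma, so chance imbalance in those measures can remain. Anyone with a change score already has the pre-test value, so the extra precision needs no new participants or data.

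**Working it through.** **Inputs from the documents.** Four arms of 25; active-versus-sham contrasts on change; 80% completion benchmark, hence 20 per arm as a lower case.

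**Assumptions.** Two-sided alpha .05 and 80% power (the plan states neither for these contrasts); r from .3 to .9; s = post SD / pre SD, taken as 1 and then varied. The plan gives no power for these contrasts, so it has no figure of its own to reproduce.

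**1. Variance ratio.** In units of the pre-test variance, change has within-arm variance 1 + s² − 2rs. The covariate model has residual variance s²(1 − r²). Hence

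ratio = s²(1 − r²) / (1 + s² − 2rs),

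which is (1 + r)/2 at s = 1. The ratio equals 1 when the slope rs = 1. It applies to every contrast among arms, including the dose trend.

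**2. Cost of estimating the slope.** The variance inflation is 1/(N − G − 2) for G arms in the model.
- Pooled, four arms: 1/94 = 1.1% with 100 analysed; 1/74 = 1.4% with 80.
- Each pair fitted alone: 1/46 = 2.2% with 50; 1/36 = 2.8% with 40.

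**3. Detectable difference as written.** The standard error of a contrast, in SD-of-change units, is sqrt(2/25) = .283. With 96 df, (1.985 + .845) × .283 = .80.

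**4. With the covariate (s = 1, pooled model, cost included).** Multiply by sqrt(ratio × 1.011). At r = .5 this is .80 × sqrt(.758) = .70.

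| r | ratio | SE reduction after cost | detectable, 25 per arm (.80 as written) | equivalent arm size on change | detectable, 20 per arm (.90 as written) |
|---|---|---|---|---|---|
| .3 | .65 | 19% | .65 | 38 | .73 |
| .5 | .75 | 13% | .70 | 33 | .78 |
| .7 | .85 | 7% | .74 | 29 | .83 |
| .8 | .90 | 5% | .76 | 27 | .86 |
| .9 | .95 | 2% | .78 | 26 | .88 |

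**5. Unequal SDs (ratio before cost, r = .3/.5/.7/.8/.9).**
- s = 1.25: .78/.89/.98/1.00/.95. At r = .8 the slope is .8 × 1.25 = 1, so nothing is gained and the 1.1% cost remains. At r = .7 the gain is negligible.
- s = 0.8: .50/.57/.63/.64/.61.

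**6. Illustration of power.** For a between-arm difference of .534 SD of change, power is 46% as written. It is 64/58/53/50/48% with the covariate at r = .3/.5/.7/.8/.9 and s = 1, before the cost, which takes off about half a point. The value .534 is borrowed from a within-arm target; it is not the plan's target for this contrast. Simulation (8,000 trials per setting) gave 63/57/51/50/48% against 45–47%. Type I error was 4.7–5.8% for both methods in 4,000 null trials per setting.

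**7. The go/no-go.** If f were read from the covariate model, it would be multiplied by sqrt(2/(1 + r)). An f of .16 on change becomes .198/.185/.174/.164 at r = .3/.5/.7/.9. A simulation (4,000 trials per setting; f as the root of effect over error sum of squares; true f of .16 on change; means rising linearly with dose; s = 1) compared the two sources:

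| r | f ≥ .16 from change | f ≥ .16 from covariate model | decisions differ | same top active arm |
|---|---|---|---|---|
| .3 | 76% | 84% | 19% | 78% |
| .5 | 77% | 83% | 15% | 81% |
| .7 | 76% | 79% | 12% | 86% |
| .9 | 76% | 78% | 6% | 91% |

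The top arm here is ranked by mean change or by adjusted mean. Which analysis feeds the decision therefore matters.

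**The case against.** **The change analysis is not wrong.** A reader might infer that omitting the baseline covariate biases the contrasts. It does not: under randomisation with complete data both analyses are unbiased. Nor does the plan forbid a covariate. This is a precision gain, and that limit stands.

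**The gain may be small.** r and s are unknown. At r = .7 to .9 with equal SDs the standard error falls by only 7% to 2%, and at r = .7 to .8 with s = 1.25 there is practically nothing to gain. This also stands. Against it, the worst case in a pooled model is a loss of about 1% of variance; with equal SDs the covariate loses only if r exceeds about .98.

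**The cost is not always 1%.** The plan's wording would allow each active-sham pair to be fitted alone, at a cost of 2% to 3%. This is why the fix specifies one pooled model.

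**The go/no-go.** A reader might infer that adding the covariate leaves the phase transition untouched. The documents do not support that by themselves. The .16 target directly follows the omnibus test in the Primary Objective. The transition paragraph names neither the model that yields f, nor the analysis that confirms direction, nor the effect size that ranks the strengths. The objection is right, and the fix must settle all three.

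**Two models side by side.** Adjusted contrasts and an unadjusted omnibus test can disagree. That is tolerable if each has a stated role, but the repeated-measures ANOVA cannot be called a sensitivity analysis while it supplies f.

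**Conclusion.** The point holds as a recommended, nearly free improvement in precision; it does not show bias or an invalid analysis. With equal SDs and r from .3 to .9, the detectable active-versus-sham difference at 25 per arm drops from .80 to .65–.78 SD of change. That equals the precision of a change analysis with about 38 down to 26 per arm. The gain is larger if the post-test SD is the smaller one, and vanishes when the slope of post on pre is near 1.

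The size rests on assumed r, SD ratio, alpha and power, none of which the documents give for these contrasts. The direction of the gain is secure except near slope 1. The benefit is confined to contrasts between arms. That the go/no-go is unaffected is a condition to be written in, not a feature of the present text.

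**What to change.** **In STATISTICAL METHODS, Primary and Secondary Objective:**
- Take the active-versus-sham contrasts and the polynomial dose trend from one pooled four-arm model of the post-test measure on treatment group. The covariate is the pre-test value of the same per-person measure from which the change would be formed.
- Use the same model for the Inc-Con accuracy and reaction-time contrasts.
- Keep the repeated-measures ANOVA as the stated omnibus analysis and the source of f.
- Keep the within-arm post-versus-pre tests and d_z as written.

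**In R61 to R33 Phase Transition Criteria:** state that f, the positive-direction check and the effect size that ranks the current strengths all come from the unadjusted analyses, and name the analysis that supplies each.

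**Cost:** wording in these two places, fixed before any group-level analysis. No new data, visits or participants. One error degree of freedom, about 1.1% of variance with 100 analysed and 1.4% with 80.
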